### Primary Endpoint Analysis

Changes in our primary outcome of interest, anxiety as measured by the Beck anxiety inventory (BAI), will be assessed using a linear mixed effect model with intervention group as the fixed effect between-subjects factor of interest and repeated measurements (baseline, 6 weeks, 12 weeks) within-subjects of the anxiety inventory as the primary dependent variable. Individual participants will be initially modeled as a random effect including both an intercept term and, if necessary, slope. The random effect for slope will be removed for an intercept only model if the random slope does not substantively improve the model or if there are issues with model fitting. Fixed effects covariates for any sociodemographic or clinical variables that differ between groups despite randomization can be added.

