## Sample Size

Using the estimating equations of Diggle et al. (2002) and based on three assessments for primary and secondary outcomes and a correlation of outcome measures over the duration of the study within individuals of 0.4, a total of 38 participants are needed per group to detect an effect size of 0.5 SD with 80% power at an  $\alpha=0.05$  (as calculated in SAS 9.3 using relevant formula). Assuming an 10% dropout rate our sample size would need to be adjusted to  $38/(1-0.1)=43$  per group using the formula from Friedman et al. (2010). A 0.5 SD difference on the anxiety inventory should represent a clinically significant effect. A corresponding change of similar magnitude on the better studied Hamilton Depression Rating Scale (not used in this study) has been considered clinically significant (Hegerl et al. 2012). Similarly, we are powered to detect clinically significant effects for the secondary outcomes of vascular function. We will

assess large vessel measures (e.g. pulse wave velocity), resistance vessel measures (forearm blood flow), and microvascular measures in the retina. In a study of brachial artery flow-mediated dilation (FMD), a reduction in FMD of 0.66 SD was associated with a 30% increased risk of cardiovascular events (Shimbo D et al. 2007). Similar results were seen in another population-based study wherein each 0.66 standard deviation in FMD was associated with an 18% increased risk of composite cardiovascular events and 36% increase risk of myocardial infarction, resuscitated cardiac arrest or coronary heart disease death (Yeboah J et al. 2009). Thus, we should be powered to detect clinically significant changes in vascular function.

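### The primary model keeps or drops its random slope on an undefined look at the data; if the target is the 12-week change and people differ in slope, dropping it makes the standard error too small

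*Combined protocol and SAP*

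**What the plan says.** The Primary Endpoint Analysis section states that "anxiety as measured by the Beck anxiety inventory (BAI), will be assessed using a linear mixed effect model". The factor of interest is "intervention group as the fixed effect between-subjects factor of interest", and the outcome is "repeated measurements (baseline, 6 weeks, 12 weeks) within-subjects of the anxiety inventory as the primary dependent variable". Participants are "initially modeled as a random effect including both an intercept term and, if necessary, slope". The section then gives two grounds for simplifying. The first is "The random effect for slope will be removed for an intercept only model if the random slope does not substantively improve the model"; the second is "if there are issues with model fitting".

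The section opens by speaking of changes in the primary outcome. It names no group-by-time term and no visit-specific contrast. It gives no test, threshold or information criterion for keeping the slope, no definition of a fitting problem and no robust standard error. It does not say whether the choice is made before the treatment result is seen.

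The Sample Size section assumes "a correlation of outcome measures over the duration of the study within individuals of 0.4": one value for all visit pairs. The Secondary Endpoint Analysis section carries the same modelling approach over to the secondary outcomes.

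**The concern.** Two analysts following this text could fit different covariance models to the same data and report different standard errors and p-values for the primary endpoint.

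The choice is not always harmless. A random-intercept-only model treats all visit pairs as equally correlated. If people change at different rates, baseline and 12 weeks are less correlated than adjacent visits. The model averages the correlations, so it credits the 12-week change with more precision than it has. For that contrast the error runs towards false positives. Moderate slope variation, large enough to matter, is also what a keep-or-drop test often misses.

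**Working it through.** **Inputs.** From the documents: three visits; a single correlation of 0.4; effect 0.5 SD; 80% power; alpha 0.05; 10% dropout; 2:1 allocation; 150 enrolled. Assumed, because the documents give no visit-specific correlations or slope variance: equal variances with correlations (baseline–6 weeks, baseline–12 weeks, 6–12 weeks) of 0.45/0.30/0.45, mean 0.40 as in the plan, or 0.50/0.30/0.50, mean 0.433 and so slightly above it; and, as a second parametrisation, a range of slope variance.

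**Step 1: the plan's own figure.** For a time-averaged difference under equal correlation, n per group = 2(z₀.₉₇₅ + z₀.₈₀)²[1 + (m−1)ρ]/(m d²). With m = 3, ρ = 0.4, d = 0.5, this is 2 × 7.849 × 1.8/0.75 = 37.67, so 38. Dropout: 38/0.9 = 42.2, so 43. Both reproduce (two-sided).

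**Step 2: intercept-only model, complete data.** The model takes the residual variance as 1 − r̄, where r̄ is the mean correlation. The ratio of true to model variance for 12 weeks minus baseline is (1 − r₀,₁₂)/(1 − r̄). The type I error is 2[1 − Φ(1.96/√ratio)]. The ratio for the 6-week change is (1 − r₀,₆)/(1 − r̄).

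| Comparison between groups | 0.45/0.30/0.45 | 0.50/0.30/0.50 |
|---|---|---|
| 12 weeks minus baseline | 0.70/0.60 = 1.17; 7.0% | 0.70/0.567 = 1.24; 7.8% |
| 6 weeks minus baseline | 0.55/0.60 = 0.92; 4.1% | 0.50/0.567 = 0.88; 3.7% |
| Joint group-by-visit test, 2 df | 5.1% | 5.2% |
| Average over visits | ratio 1.00; 5.0% | ratio 1.00; 5.0% |

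The joint test stays near nominal because it combines the linear contrast (ratio 1.17 or 1.24) with the quadratic contrast (ratio 0.83 or 0.76), and the two nearly cancel. With exactly equal correlations every ratio is 1.

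**Step 3: the same in terms of slope variance.** Let t be the slope variance per 6-week unit and s the residual variance. The true variance of the 12-week change is 4t + 2s; the intercept-only model uses 2t + 2s. With mean variance 1 and mean covariance 0.4, s = 0.6 − t.

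| t | baseline–12-week correlation | variance ratio | SE too small by | type I error |
|---|---|---|---|---|
| 0 | 0.40 | 1.00 | 0% | 5.0% |
| 0.1 | 0.32 | 1.4/1.2 = 1.17 | 7% | 7.0% |
| 0.2 | 0.25 | 1.6/1.2 = 1.33 | 13% | 9.0% |
| 0.3 | 0.18 | 1.8/1.2 = 1.50 | 18% | 11% |
| 0.6 (no residual variance) | 0 | 2.4/1.2 = 2.00 | 29% | 16.6% |

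**Step 4: the keep-or-drop rule.** The plan gives no criterion, so a likelihood-ratio test (cut 5.99) and AIC stand in for it.

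- Correlation scenarios, 90:45 (150 less 10%, split 2:1), 1,200 simulated covariance estimates each. At 0.45/0.30/0.45 the likelihood-ratio rule drops the slope in 61% of trials, and overall error for the 12-week change is 6.0%. At 0.50/0.30/0.50 overall error is 5.7%. An unstructured covariance gives 5.0% in both.
- Slope-variance scenarios, 3,000 trials each, for the 12-week change:

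| t, group sizes | intercept-only always | likelihood-ratio rule (dropped) | AIC rule (dropped) |
|---|---|---|---|
| 0.1, 43:43 | 7.1% | 6.2% (73%) | 5.8% (57%) |
| 0.1, 100:50 | 6.6% | 5.6% (59%) | 5.2% (39%) |
| 0.2, 43:43 | 8.6% | 5.0% (20%) | 4.7% (9%) |
| 0.2, 100:50 | 9.6% | 5.2% (3%) | 5.1% (1%) |

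Always keeping the slope gave 4.3% to 5.1% across all settings. The group main effect under the intercept-only model gave 4.6% to 5.8%. Monte Carlo error is about 0.4 points at 5%.

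**The case against.** The plan starts from the richer model and simplifies it, which is ordinary mixed-model practice, and it names a fallback. Any sensible test largely corrects itself: a large slope variance is detected and kept, so in the simulations overall error never exceeded 6.2%. The effect the plan literally names is intervention group, and the sample size formula is for a time-averaged difference. For that effect the intercept-only standard error is right. The one correlation in the plan, 0.4, fits equal correlation; the decay is an assumption of this review.

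All of this stands as a limit on the size of the problem. A reader might infer that dropping the slope always understates the error of the primary comparison, or can only do so when correlations decay. The documents do not support either statement. They name no 12-week contrast and give no evidence of decay, and under the same decaying correlations the other comparisons are exact, near nominal or conservative.

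Two things remain. First, the 12-week change is still a reasonable target: the section speaks of changes, baseline is among the modelled outcomes although the workshop cannot affect it, and the last assessment is at 12 weeks. Second, the ground "if there are issues with model fitting" does not depend on the size of the slope variance, so the protection that a test gives does not extend to it.

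**Conclusion.** The concern holds in conditional form, as a low-priority improvement. That the keep-or-drop rule has no criterion is plain from the text. The understated standard error needs three further things: the primary comparison is the baseline-to-12-week change, people differ in slope, and the slope is dropped. Then the intercept-only model has 7.0% or 7.8% type I error under the two assumed correlation patterns. Under an ordinary likelihood-ratio rule with moderate slope variance, overall error is about 5.6% to 6.2%. The larger figures, 9% to 11% at t = 0.2 to 0.3, apply only if a fitting problem or a loose reading of the rule removes a large slope variance.

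These figures assume complete, normally distributed data and the same covariance in both arms, and they ignore clustering by workshop. The 38 and 43 per group are not in question.

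**What to change.** Replace the selection step by one fixed specification:

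- visit as a categorical factor with group-by-visit terms;
- one named group contrast as primary (the 12-week change, if that is what is meant);
- an unstructured 3x3 within-person covariance with small-sample degrees of freedom;
- one named fallback, for example heterogeneous Toeplitz with robust standard errors, used only on non-convergence.

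The choice of fallback is a matter of preference; naming it in advance is what counts. If the team prefers to keep the random-slope model, the minimum is to state the numerical keep-or-drop criterion, define a fitting problem, and name the contrast.

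The cost is SAP wording. Six covariance parameters are easily estimated from about 135 completers (150 × 0.9). If correlations really are equal, the loss of efficiency is negligible.

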## Randomization

A statistician will develop a computer program in R that will generate a 2:1 randomization for the ACT intervention group versus the control group, respectively.

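### The primary BAI model adds covariates only if the arms happen to differ, and only optionally; the cost depends on a contrast that is not fixed and on how baseline BAI is used

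*Combined protocol and SAP*

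**What the plan says.** Under Primary Endpoint Analysis, BAI is analysed with a "linear mixed effect model with intervention group as the fixed effect between-subjects factor of interest". The response is described as "repeated measurements (baseline, 6 weeks, 12 weeks) within-subjects of the anxiety inventory as the primary dependent variable", so baseline BAI is one of three outcome values and not a covariate. No time term, group-by-time term or constraint on the baseline means is stated.

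Covariates are covered by one sentence: "Fixed effects covariates for any sociodemographic or clinical variables that differ between groups despite randomization can be added". No candidate variables, test or threshold are named, and the wording permits adjustment without requiring it.

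Nothing elsewhere fills the gap. Randomization says only that a program will "generate a 2:1 randomization for the ACT intervention group versus the control group, respectively", with no stratification factor. Descriptive Analyses plans baseline summaries only. Secondary Endpoint Analysis does make confounder adjustment mandatory, but for the regressions on change in anxiety, not for the randomised comparison.

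**The concern.** Under randomisation, an observed baseline difference is a chance event. Screening for such differences does not find the variables that predict BAI: a strong predictor that happens to be balanced stays out, and an irrelevant variable that happens to be imbalanced may go in. Because entry is optional and a difference is undefined, at least two primary models remain available once the data are seen.

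The candidate pool is wide. Visit 1 collects demographics, health history, medications, sleep and activity surveys and eight online questionnaires. At stake are the prespecification of the primary result and, depending on the contrast, its precision.

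**Working it through.** **1. The plan's own figure.** Inputs from Sample Size: "based on three assessments for primary and secondary outcomes" (m = 3), "a correlation of outcome measures over the duration of the study within individuals of 0.4" (ρ = 0.4), and "a total of 38 participants are needed per group to detect an effect size of 0.5 SD with 80% power" with α = 0.05.

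- Variance factor for the mean of m visits: f = [1 + (m − 1)ρ]/m = (1 + 0.8)/3 = 0.60.
- n per group = 2(1.960 + 0.842)² f / d² = 62.8 f = 62.8 × 0.60 = 37.7, so 38 (two-sided). This matches. One-sided gives 30, which does not.
- Dropout: 38/0.9 = 42.2, so 43. This matches.

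No covariate enters this formula, so the 38 and 43 are untouched by the point.

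**2. How often the rule would be triggered.** Assume that a difference means p < 0.05 and that the variables are independent (neither is in the documents). The chance that at least one of k variables is flagged is 1 − 0.95^k: 23% for k = 5, 40% for k = 10, 64% for k = 20.

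**3. What covariates do under each contrast.** Take 150 randomised 2:1, less 10%, giving 90:45. Then SE = √[f(1/90 + 1/45)] = √(f/30) in SD units.

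- *Group main effect over three visits.* f = ρ + (1 − ρ)/3 = 0.4 + 0.2 = 0.60 and SE = √0.02 = 0.141. Between-person variance (0.4) is part of f, so person-level covariates matter. In simulated trials with six covariates and an assumed R² of 0.2, adding them cut the SE from 0.141 to 0.119 and moved the estimate by up to 0.22 SD.
- *Group-by-time contrast, 12 weeks minus baseline.* f = 2(1 − ρ) = 1.2 and SE = √0.04 = 0.20. Between-person variance has cancelled, so time-constant covariates have nothing left to explain. In simulated complete data under a random-intercept model, adding them moved the contrast by less than 1e-14 and left the SE at 0.2011.

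**4. What the handling of baseline BAI does.** Outcome: mean of the 6- and 12-week scores; ρ = 0.4 at all lags; d = 0.5. No R² has to be assumed.

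| Use of baseline | Variance factor | n per group, 1:1 (62.8 f) | Power at 90:45 |
|---|---|---|---|
| Unconstrained change | (1 + ρ)/2 + 1 − 2ρ = 0.90 | 57 | 82% |
| Baseline ignored | (1 + ρ)/2 = 0.70 | 44 | 91% |
| Baseline as covariate | (1 + ρ)/2 − ρ² = 0.54 | 34 | 96% |

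Power is Φ(0.5/√(f/30) − 1.96). For f = 0.90: 0.5/0.173 = 2.89, giving Φ(0.93) = 82%. For f = 0.54: 0.5/0.134 = 3.73, giving Φ(1.77) = 96%.

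**5. Type I error.** This was simulated in a simplified single-outcome regression at 90:45, with 5 or 10 covariates and assumed R² 0.2. The rate was 4.6% unadjusted, 4.3% with the rule applied mechanically, and 5.1 to 5.3% if the better of the two results is kept. Other assumed inputs (6 to 10 covariates, R² up to 0.4) raised the better-of-two figure to at most 6.0%.

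**The case against.** The strongest reply is that the planned analysis concerns change in BAI through a repeated-measures model. For a group-by-time contrast, step 3 shows that adding age, sex or similar covariates alters neither the estimate nor its standard error when data are complete. On that reading the analyst's choice is nearly harmless, and baseline BAI, probably the most informative variable, is already in the model. The algebra is correct and this part stands. It fails if the test is the group main effect, if covariates interact with time, or if enough data are missing. The section names no time or group-by-time term, so the harmless reading is not secured. Having baseline BAI among the outcomes gives the precision in the last row of the table only if baseline means are constrained to be equal, which is not stated.

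Three stronger readings are tempting and not supported:

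- *That the rule costs a definite amount of power.* A reader might infer this from a regression on one post-treatment outcome with prognostic covariates. That is not the planned model, and the documents give no R² for any covariate.
- *That the trial is underpowered as a result.* The plan's own formula gives about 94% power at 90:45 (f = 0.60: 0.5/0.141 = 3.54, Φ(1.58)), although that formula counts the difference as present at all three assessments, baseline included.
- *That the primary p-value is invalid.* Step 5 shows little inflation even under deliberate selection.

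It is also fair to say that nothing in the documents shows that age, sex or medication predicts BAI.

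**Conclusion.** The point holds as one of prespecification. The plan states a covariate rule that is optional, undefined and triggered by chance imbalance, where a fixed list would serve better, and this leaves more than one primary model open after the data are seen. Its effect on type I error is small.

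The size of the effect on the estimate is conditional. Under a group main effect, covariate choice matters for both the estimate and its precision, though the amount rests on an assumed R². Under a group-by-time contrast with complete data it matters hardly at all. What can be sized from the plan's own inputs is the handling of baseline BAI: a variance factor of 0.90 v 0.54, or about 82% v 96% power at 90:45. That comparison assumes that all 150 enrolled are randomised, 10% drop out, the correlation is a constant 0.4, and the target is the mean of the two post-baseline visits. The change should be made, but the plan is not unsound without it.

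**What to change.** Delete the imbalance-triggered sentence and, before unblinding, put in its place:

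1. The contrast that is the primary test.
2. One treatment of baseline BAI: either a covariate with only the 6- and 12-week scores as outcomes, or a model over all three visits that constrains the baseline means to be equal. It should not be both an outcome and a covariate.
3. A short fixed list of covariates already collected, included whatever the observed balance. Age, sex and stable antidepressant or anxiolytic use are examples: demographics and current medications are recorded at Visit 1, and stable users of these drugs are eligible. The choice belongs to the study team.
4. Unadjusted or imbalance-driven models reported only as sensitivity analyses.

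The cost is a few sentences of text and a few degrees of freedom. No new data, visits or participants are needed.

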### Secondary Endpoint Analysis

State and Trait subscales of the STAI will be secondarily modeled as the dependent variable to assess changes in the domains of trait and state anxiety.

The novel physiological variables (vascular function, mSNA, inflammation) will serve as secondary outcomes and will be explored in analogous to the above. We will also assess for any relationship between these variables and changes in anxiety across groups in linear regression models (since these physiological variables are only measured at two points, there is no need for linear mixed models). For these latter analyses, variables for relevant sociodemographic and clinical confounds will need to be included as change in anxiety is not assigned by randomization akin to group assignment. Comparisons between the groups of higher anxiety and low anxiety will be made using one-way analysis of variance to determine differences in vascular function, mSNA, and inflammation. Baseline values for the higher anxiety group will be compared to the values obtained from the low anxiety group during their one-time experimental visit.

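### For physiological outcomes measured only at Visits 2 and 4, the carried-over model states no baseline adjustment: depending on how it is read, it halves the 12-week effect or gives up precision the Visit 2 value would supply.

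*Combined protocol and SAP*

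**What the plan says.** Secondary Endpoint Analysis states that the physiological variables "will serve as secondary outcomes and will be explored in analogous to the above". It gives no formula, so the model is the one under Primary Endpoint Analysis. That section has "intervention group as the fixed effect between-subjects factor of interest" and takes "repeated measurements (baseline, 6 weeks, 12 weeks) within-subjects of the anxiety inventory as the primary dependent variable". Baseline is therefore a response. No visit term, group-by-visit term, baseline covariate or equal-baseline constraint is stated. On random effects it says: "Individual participants will be initially modeled as a random effect including both an intercept term and, if necessary, slope". The slope is dropped if it does not help "or if there are issues with model fitting".

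Secondary Endpoint Analysis also remarks: "since these physiological variables are only measured at two points, there is no need for linear mixed models". That remark belongs to the regressions relating physiological variables to change in anxiety, not to the comparison of randomised groups.

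The Assessment Schedule lists pulse wave velocity, carotid compliance, 24-hour blood pressure, blood markers and endothelial cell collection at Visits 2 and 4 and not at 6 weeks. Microneurography and venous occlusion plethysmography are also listed at 6 weeks. The control group follows the same schedule apart from the workshop.

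**The concern.** A three-visit template is applied to outcomes with one pre-intervention and one post-intervention value, and the template does not say which contrast is the treatment effect or how baseline enters. With two visits the choice matters: the possible readings estimate different quantities or do so with quite different precision. None of the wording commits the analysis to the efficient use of a baseline that is collected anyway.

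The outcomes affected carry the pulse wave velocity part of prediction 4, the 24-hour blood pressure part of prediction 5, and the inflammation and oxidant stress hypotheses under Research Question and Hypothesis. An open choice of contrast also leaves room to settle the analysis after the data are seen.

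**Working it through.** **Inputs.** Correlation r: "a correlation of outcome measures over the duration of the study within individuals of 0.4" (Sample Size). Effect 0.5 SD, alpha 0.05, 10% dropout (Sample Size). Enrolment 150 (Description of Study Population) at 2:1 (Randomization). If all 150 are randomised, that is 100 versus 50, and 90 versus 45 after 10% dropout. Assumed here: two-sided test, normal approximation, equal variance at both visits, complete pairs among those analysed.

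**The plan's own figure.** For a time-averaged difference over m = 3 assessments, n per group = 2(1.960 + 0.842)² × [1 + (m − 1)r] / (m × 0.5²) = 2 × 7.849 × 1.8 / 0.75 = 37.7, rounded up to 38. Then 38/0.9 = 42.2, rounded up to 43. Both stated figures reproduce. They rest on three assessments; the outcomes discussed here have two.

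**What the carried-over model estimates with two visits.** Variance is given as a multiple v of σ²(1/n₁ + 1/n₂).

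1. Group main effect, no interaction: it compares two-visit means. v = (1 + r)/2 = 0.70. Randomisation implies no expected difference at baseline, so a 12-week effect of 0.5 SD appears as (0 + 0.5)/2 = 0.25 SD.
2. Group-by-visit term, free baseline means: identical to the change score. v = 2(1 − r) = 1.20.
3. Visit 4 value with the Visit 2 value as covariate, or a mixed model with a common baseline mean: v = 1 − r² = 0.84.

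A generalised least squares calculation for two visits gave 0.70 for the main effect, 1.20 for the interaction and 0.84 for the common-baseline model.

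**Power with 90 versus 45.** 1/90 + 1/45 = 0.0333, SE = √(0.0333v), power = Φ(effect/SE − 1.96).

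| Model | SE (SD units) | Effect estimated | Power at 0.5 SD |
|---|---|---|---|
| Group main effect | 0.153 | 0.25 | 37% |
| Change score | 0.200 | 0.50 | 70.5% |
| Baseline-adjusted | 0.167 | 0.50 | 84.8% |

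**At 0.66 SD**, the figure that Sample Size cites for vascular function, the change score gives 0.66/0.200 = 3.30, so Φ(1.34), about 91%. Baseline adjustment gives 0.66/0.1673 = 3.94, so Φ(1.98), about 98%. The main effect gives 0.33/0.1528 = 2.16, so Φ(0.20), about 58%.

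**Dependence on the correlation.** The saving over the change score is 1 − (1 − r²)/[2(1 − r)] = (1 − r)/2.

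| r | Change score v | Adjusted v | Saving |
|---|---|---|---|
| 0.2 | 1.60 | 0.96 | 40% |
| 0.4 | 1.20 | 0.84 | 30% |
| 0.6 | 0.80 | 0.64 | 20% |
| 0.8 | 0.40 | 0.36 | 10% |

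**Random slope.** Intercept variance, slope variance, their covariance and the residual are four parameters. Two visits supply two variances and one covariance, three quantities in all, so the four cannot be separated. With three visits they can.

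**The case against.** The strongest reply is that the plan does not commit to an inefficient analysis. It never states a group-by-visit term, so the change-score equivalence is only one reading. The same mixed model with a common baseline mean has multiplier 0.84 and loses nothing. Specifying contrast and baseline handling in the primary model could also carry over. This is right as far as it goes: the defect is an unspecified model, not a wrong one. But the common-baseline version is not written down, and the literal wording points to the main effect, the worst of the three.

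A reader might infer that the model cannot be fitted at all. The documents do not support that. The slope is conditional ("including both an intercept term and, if necessary, slope"), and the intercept-only fallback covers fitting failure, so no analysis is blocked.

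A reader might also take 30% as a general loss. It holds for the change-score reading at r = 0.4, a single planning value for all outcomes. Experimental Methods reports a 2.1% coefficient of variation for carotid-femoral pulse wave velocity in 7 young adults; if such measures correlate more strongly across visits, the saving shrinks towards 10% or less.

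The 0.5 SD effect is argued in Sample Size for the anxiety inventory. At the 0.66 SD cited for vascular function, the change score already exceeds 80% power. That stands and limits the consequence, though only for the change-score reading.

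Finally, the authors plainly recognised the two-visit structure, but applied ordinary regression only to the association analyses.

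**Conclusion.** The point holds for the outcomes scheduled only at Visits 2 and 4. Under the literal main-effect reading, the 12-week effect is understated by about half and power at 0.5 SD is 37%. Under the change-score reading, the comparison is valid and unbiased but less precise: 70.5% power against 84.8%, a variance saving forgone of 30% at r = 0.4 and of 40% to 10% for r from 0.2 to 0.8. These powers assume all 150 are randomised, 10% dropout, a two-sided 5% test and equal variances at the two visits.

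It would go too far to say that predictions 4 and 5 as a whole depend on this. Retinal measures are listed at Visit 1 with no listed follow-up. Heart rate variability is recorded by wristband during microneurography, which is also scheduled at 6 weeks. Muscle sympathetic nerve activity and forearm blood flow likewise have three time points, so the plan's two-point remark does not match the schedule for them and the two sections need reconciling.

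The outcomes are secondary and exploratory. The change is worth making but does not threaten the primary analysis.

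**What to change.** Under Secondary Endpoint Analysis, replace the reference to the primary model, for outcomes measured only at Visits 2 and 4, with a linear regression of the Visit 4 value on arm with the Visit 2 value as covariate. Report the adjusted arm difference with its 95% CI. A mixed model with a common baseline mean and a group difference at Visit 4 is an equivalent alternative. List the outcomes covered: pulse wave velocity, carotid compliance, 24-hour blood pressure variability, cytokines and other blood markers, and endothelial proteins. Keep muscle sympathetic nerve activity and forearm blood flow in the three-visit model, and correct the two-point remark to match the schedule.

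The cost is wording only, with no new data. The small downside is that complete-case regression drops anyone missing either visit; the common-baseline mixed model avoids this.
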